5.2.2.1 Oxaliplatin

- Oxaliplatin administration must always precede the administration of 5-FU.
- Oxaliplatin may be given at the same time as leucovorin in separate bags using a Y connector (providing trometamol is not used as an excipient).
- Oxaliplatin may not be administered with fluorouracil.
- Do not use with injection equipment containing aluminum, as this can degrade platinum compounds.
- Oxaliplatin causes irritation if extravasated (follow local policy).
- Acute neurotoxicity is common with oxaliplatin and can be precipitated on exposure to cold, therefore cryotherapy should be avoided.
- Infuse IV over 2 hours. Increasing infusion time to 6 hours may decrease acute toxicity such as pharyngolaryngeal dysesthesia.
- Unopened vials should be stored at 15-30°C; protect from light.

5.2.2.2 Leucovorin

- Leucovorin may be given at the same time as oxaliplatin in separate bags using a Y connector (providing trometamol is not used as an excipient).
- Leucovorin must be given prior to fluorouracil (enhances the effects of fluorouracil by increasing fluorouracil binding to target enzyme thymidylate synthetase).
- Infuse IV over 2 hours using CADD pump or similar device.

5.2.2.3 Fluorouracil

- Infuse through central venous access device if available. Infuse through peripheral venous catheter if infusion for only 3-5 days.
- Inspect peripheral infusion sites daily and replace if evidence of irritation or extravasation.
- Fluorouracil is incompatible with doxorubicin, epirubicin, diazepam, methotrexate, and cytarabine. Line must be flushed between administration of fluorouracil and these agents.
- Give IV bolus slow push through sidearm of free-flowing IV (D5W or NS) over 5 minutes.
- Infuse IV continuous infusion over 46 hours using CADD infusion pump or similar device.

5.3 CV301

5.3.1 MVA-BN-CV301

One MVA-BN-CV301 vaccine vial has a nominal titer of 4×10^8 infectious units (Inf.U) in 0.5 mL of the drug product. The composition of 1 dose of MVA-BN-CV301 is described below:

Component	Quantity per Dose (0.5 mL)	Function
Active substance		
Live attenuated vaccinia virus, strain MVA-BN-CV301	Nominal Titer 4×10^8 Inf.U	Active substance, immunizing antigen
Excipients		
Trometamol (Tris-hydroxymethyl-amino methane)	0.605 mg (10 mM)	Excipient Component of formulation buffer
Sodium Chloride	4.090 mg (140 mM)	Excipient Component of formulation buffer

5.3.2 FPV-CV301

One FPV-CV301 vaccine vial has a nominal virus titer of 1×10^9 Inf.U in 0.5 mL of the drug product. The composition of 1 dose of FPV-CV301 is described below:

Component	Quantity per Dose (0.5 mL)	Function
Active substance		
Live recombinant vaccinia virus, strain FPV-CV301	Nominal Titer 1×10^9 Inf.U	Active substance, immunizing antigen
Excipients		
Sodium Chloride	3.6 mg (123.2 mM)	Excipient Component of formulation buffer
Potassium Chloride	0.09 mg (2.4 mM)	Excipient Component of formulation buffer
Potassium Dihydrogen Phosphate	0.09 mg (1.3 mM)	Excipient Component of formulation buffer
Potassium Chloride	0.09 mg (2.4 mM)	Excipient Component of formulation buffer
Potassium Dihydrogen Phosphate	0.09 mg (1.3 mM)	Excipient Component of formulation buffer

Detailed trial-specific instructions on the preparation and administration of MVA-BN-CV301 and FPV-CV301 are provided in a separate Pharmacy Manual supplied to each clinical trial site.

5.3.3 CV301 Dosing

The following dosing is based on the experience in a phase I clinical trial. Trial CV301-2015-201 is an ongoing, BN-sponsored Phase 1/2 Trial of CV301 in Combination with Nivolumab versus Nivolumab in Subjects with Previously Treated Non-Small Cell Lung Cancer.

In the phase I part of this trial, 12 subjects with various CEA/MUC-1 positive cancers have been enrolled, 6 male and 6 female subjects, aged between 39 and 77 years. Of these 12 subjects, 3 have received MVA-BN-CV301 at the lowest dose level, 4×10^8 Inf.U., 3 have received the second dose level, 8×10^8 Inf.U., and 6 have received the highest dose level, 1.6×10^9 Inf.U.

At the cut-off date for assessment of the initial phase I safety data, 3 of the subjects had also received at least one dose of FPV-CV301, at a dose of 1×10^9 Inf.U./0.5 mL.

Initial safety data from the phase I part of this trial involving 12 subjects dosed in three different dose levels show that almost all reported AEs refer to expected (solicited) local and general reactions, including injection site reactions, fever/chills, headache, fatigue, myalgia/arthralgia, and flu-like symptoms. There was no occurrence of any of the pre-specified adverse events of special interest (immune-related events and cardiac events). There were no related SAEs. There were no dose-limiting toxicities at all three investigated dose levels of MVA-BN-CV301. Based on this initial safety information, the trial has moved into the phase Ib part, which includes combination treatment of CV301 and Nivolumab. The selected dose level for the further course of the trial was 1.6×10^9 Inf.U. (i.e. 4 injections of 4×10^8 Inf.U./0.5 mL) of MVA-BN-CV301.

5.3.4 MVA-BN-CV301

The dose for MVA-BN-CV301 is 4 injections of 4×10^8 infectious units/0.5 mL given subcutaneously prior to the start of nivolumab on Days -28 and -14. All injections will be given at the same clinic visit.

5.3.5 FPV-CV301

The dose for FPV-CV301 is 1 dose of 1×10^9 infectious units/0.5 mL given subcutaneously prior to the start of nivolumab at least one hour prior to mFOLFOX6 on Day 1 of Cycles 1-4, and FVP-CV301 boosters given every 2 weeks through completion of chemotherapy on Cycles 5-12, FVP-CV301 will then be administered every twelve weeks.

5.4 Nivolumab Dosing

Nivolumab is safe and well tolerated up to 10mg/kg Q2W. For this study, the standard every 2-week Nivolumab dose of 240 mg IV (identical to a dose of 3 mg/kg for subjects weighing 80 kg) was selected based on clinical data, modeling and simulation approaches using population PK and exposure-response analyses of data from studies in multiple tumor types (melanoma, NSCLC, and renal cell carcinoma) where body weight normalized dosing (mg/kg) has been used. Pre-operatively, participants will receive nivolumab at a dose of 240 mg as a 30 minute infusion every 2 weeks (starting with chemotherapy in the control arm Cycles 1-4 and starting with the vaccine in the experimental arm Days -28, -14 then Cycles 1-4). Post-operatively nivolumab will be given at a dose of 240 mg IV every 2 weeks concurrently with chemotherapy \pm vaccine for 8 chemotherapy cycles (Cycles 1-8). After Cycle 8 (completion of chemotherapy), nivolumab will be given concurrently with the vaccine. Nivolumab will be given every 4 weeks at the standard every 4-week dosing of 480 mg IV for up to 24 cycles and the vaccine will be given every 12 weeks. An infusion window of \pm 10 minutes may be applied.

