4. SUBJECT REGISTRATION

This protocol is open to both men and women and all races. All subjects must be registered through HCRN's electronic data capture (EDC) system. A subject is considered registered when an "On Study" date is entered into the EDC system. Subjects must be registered and randomized prior to starting protocol therapy. Subjects must begin therapy **within 5 business days** of randomization.

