5.1.2 Neoadjuvant Therapy

Patients who are eligible for and consent to enroll onto this trial will be randomized to either the control arm or the experimental arm. One cycle is 2 weeks.

- Patients in the control arm (Arm A) will receive mFOLFOX6 and Nivolumab given on Day 1 of every 2 week cycle for 4 cycles (Cycle 1 - Cycle 4). The treatment order for Arm A is Nivolumab followed by mFOLFOX6.
- The experimental arm (Arm B) will receive two doses of Nivolumab and MVA-CV301 each given Days -28, -14, followed by four cycles of Nivolumab plus FPV-CV301 given on Day 1 of every 2 week cycle concurrently with mFOLFOX6, which will again be administered every 2 weeks for 4 cycles (Cycle 1 – Cycle 4). For Arm B the order of administration is Nivolumab followed by the vaccination at least one hour prior to mFOLFOX6.

A window of +2 days between administration of Nivolumab +/- vaccination and mFOLFOX6 is allowed. This window will accommodate subjects that receive their chemotherapy locally. If there is more than a 2-day delay for any reason, administration of study drugs should be re-aligned so that the chemotherapy falls within +2 days with the next cycle.

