12. STATISTICAL METHODS

12.1 Study Design

This is a multi-center, 1:1 randomized clinical trial comparing CV-301 vaccine to standard treatment in patients with resectable hepatic metastatic colorectal cancer.

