12.2 Objectives and Endpoints

12.2.1 Definition of Primary Objective and Endpoint

Primary objective: We hypothesize that the addition of vaccination with CV301 to Nivolumab and perioperative systemic chemotherapy followed by complete surgical resection in patients with hepatic-limited metastatic colorectal cancer will significantly increase OS as compared to Nivolumab and perioperative systemic chemotherapy followed by surgical resection.

Primary Endpoint: 3-year OS between perioperative mFOLFOX6 plus Nivolumab and CV301 in combination with surgical resection in patients with hepatic-limited metastatic colorectal cancer. For the primary objective OS is defined as the date of metastasectomy to date of death from any cause.

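### Arm B is not Arm A plus CV301: it also has two more pre-operative nivolumab doses and a chemotherapy start about four weeks later, so Section 12 should claim a regimen effect, not a CV301 effect.

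*Combined protocol and SAP*

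**What the plan says.** Section 5.1.2 sets out the neoadjuvant phase. Arm A "will receive mFOLFOX6 and Nivolumab given on Day 1 of every 2 week cycle for 4 cycles (Cycle 1 - Cycle 4"). Arm B receives "two doses of Nivolumab and MVA-CV301 each given Days -28, -14, followed by four cycles of Nivolumab plus FPV-CV301", with mFOLFOX6 given in those same four cycles. Section 5.4 agrees: nivolumab 240 mg every two weeks begins with chemotherapy in Arm A, and in Arm B it is given "starting with the vaccine in the experimental arm Days -28, -14 then Cycles 1-4". The Synopsis and the Section 7 calendar show the same difference, so the text in 5.4 is not itself an error.

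Section 4 applies one start rule to both arms: "Subjects must begin therapy within 5 business days of randomization". Section 5.1.3 places surgery about four weeks after neoadjuvant therapy ends, again in both arms. After surgery the planned nivolumab is the same in each arm: "Post-operatively nivolumab will be given at a dose of 240 mg IV every 2 weeks concurrently with chemotherapy" for eight cycles, then 480 mg every four weeks for up to 24 cycles.

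The claim to be tested is in Section 12.2.1: "We hypothesize that the addition of vaccination with CV301 to Nivolumab and perioperative systemic chemotherapy" will increase OS. Section 12.1 describes the trial as "comparing CV-301 vaccine to standard treatment in patients with resectable hepatic metastatic colorectal cancer", and Section 12.3 repeats that sentence. No section lists the nivolumab or timing difference as a limitation on what may be concluded.

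**The concern.** A hypothesis about adding CV301 needs arms that differ only in CV301. Here three things change together: the vaccine, two nivolumab doses given before any chemotherapy, and the time from randomisation to chemotherapy and surgery. With two arms (Section 4.1) and a log-rank test (Section 12.7), no analysis of these data can separate them.

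The plan gives reasons not to treat the other components as inert. Section 1.1 argues that CV301 combined with anti-PD-1 therapy may be more efficacious than either alone, which treats PD-1 blockade as potentially active. The same section says the earlier non-randomised vaccine result needs validating against a randomised control before phase III, so attribution is central to the trial's purpose.

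The whole imbalance falls before surgery. It therefore also bears on pre-operative response and pathologic response (Section 2.2) and on the pre- versus post-therapy biomarker comparisons (Section 2.3).

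**Working it through.** **The plan's own power figure (background, not in dispute).** Inputs from 12.3: 3-year OS 58.8% versus 88.7%, 35 resected patients per arm, one-sided 2.5% log-rank test, 80% power. Under exponential survival, HR = ln(0.887)/ln(0.588) = 0.226. Freedman's formula gives (1.960 + 0.842)² × ((1 + 0.226)/(1 − 0.226))² ≈ 19.7, so 20 deaths, with power 80.6% at 20. The stated 80% reproduces.

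**Nivolumab doses (5.1.2, 5.1.4, 5.1.5, 5.4).** Section 5.4 numbers the post-operative cycles 1–8 and 5.1.4 numbers them 5–12; the count is eight either way.

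| Phase | Arm A | Arm B |
|---|---|---|
| Pre-operative, 240 mg | 4 | 2 + 4 = 6 |
| Adjuvant, 240 mg | 8 | 8 |
| Maintenance, 480 mg (maximum) | 24 | 24 |
| Total doses | 36 | 38 |

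- Pre-operative: 4 × 240 = 960 mg versus 6 × 240 = 1440 mg; 1440/960 = 1.5, or 50% more.
- Full plan: 12 × 240 + 24 × 480 = 14,400 mg versus 14 × 240 + 24 × 480 = 14,880 mg; 480/14,400 = 3.3% more.

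**Timing (4, 5.1.2, 5.1.3).** This is inferred; the documents do not state a delay in so many words. Both arms start within five business days of randomisation. Arm A's first treatment is Cycle 1 with mFOLFOX6. Arm B's is Day −28, so its mFOLFOX6 comes about 28 days later. Counting four full two-week cycles and about four weeks to surgery:

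- Arm A: 8 + 4 = about 12 weeks.
- Arm B: 4 + 8 + 4 = about 16 weeks.

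Counting from the last dose instead of the end of Cycle 4 lowers both totals equally. The four-week gap remains.

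**What an unseparated component could do (illustration).** The documents give no survival effect for the extra nivolumab or the later chemotherapy, so the HR below is an assumption. Suppose CV301 has no effect and the other differences together have hazard ratio h. At the plan's 22 expected deaths (12.8), using Schoenfeld's approximation and ignoring the interim look, the probability of one-sided significance at 2.5% is Φ(−√(22/4) × ln h − 1.960).

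| Assumed h | Probability of significance |
|---|---|
| 1.25 | 0.7% |
| 1.10 | 1.5% |
| 1.00 | 2.5% |
| 0.95 | 3.3% |
| 0.90 | 4.3% |
| 0.80 | 7.5% |
| 0.70 | 13.1% |

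Significance at 22 deaths needs an observed HR of about exp(−1.960 × 2/√22) = 0.43. The non-vaccine differences alone would need a true HR near that value to give even a 50% chance of a positive test.

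**The case against.** The strongest reply is that the lead-in is part of the vaccine strategy. The MVA prime on Days −28 and −14 comes before the common cycles by design, and giving it with nivolumab fits the PD-1 rationale in Section 1.1. The later chemotherapy start then belongs to the intervention, and a net effect including any harm from delay is the right result for that strategy. This stands for the timing. It is weaker for the two nivolumab doses, which are not vaccine. It is also an argument for a regimen-level claim, which is what 12.2.1 should then say.

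Other parts of the reply also stand:

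- The objective in 2.1 is already close to regimen level, because it names CV301 in combination with the other components on one side and the control regimen on the other. The problem sits mainly in 12.1, 12.2.1 and 12.3.
- The excess is 2 of 38 planned doses, and nothing in the documents suggests an effect large enough to drive the test by itself.
- Primary OS starts at metastasectomy, so the extra four weeks lie outside the primary clock, and OS from registration is a listed secondary objective. These bear on the time origin; neither helps attribution.
- The Synopsis, 5.1.2 and 12.2.1 all name nivolumab in the control arm. The term standard treatment in 12.1 and 12.3 is loose shorthand, not a misdefined comparator.

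A reader might infer that the trial is invalid, or that a CV301 claim would be wrong whether the test is positive or negative. The documents support neither. Randomisation protects the comparison of the two regimens, and an effect that cannot be separated is unproven, not false. A reader might also take the 50% pre-operative excess as the overall imbalance; over the full plan it is 3.3% by milligram.

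**Conclusion.** The point holds as one about attribution. The arms differ in pre-operative nivolumab (six versus four doses) and in time to chemotherapy and surgery (about four weeks), as well as in CV301. The design supports a conclusion about the Arm B regimen against perioperative mFOLFOX6 plus nivolumab. It does not support crediting the difference to CV301, as 12.1, 12.2.1 and 12.3 do.

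The dose counts come directly from the text. The timing difference rests on reading Section 4 together with 5.1.2 and 5.1.3. The direction and size of any non-vaccine effect are unknown: extra checkpoint inhibition could favour Arm B, and later chemotherapy could work against it. Under assumed non-vaccine hazard ratios of 0.9 to 0.7, an inert vaccine would give a positive test 4.3% to 13.1% of the time instead of 2.5%; those figures are illustrative only. This point does not disturb the sample size, the alpha or the planned test. The restriction of efficacy to completely resected patients (12.6) is a separate matter.

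**What to change.** Change wording only:

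1. In 12.1, 12.2.1 and 12.3, describe the comparison as the Arm B regimen (CV301 with a four-week nivolumab lead-in, then the common regimen with continued CV301) versus perioperative mFOLFOX6 plus nivolumab. Align 2.1 and the Synopsis objective.
2. Add to 12.2.1 or 12.7 a statement made in advance that the result will not be attributed to CV301 alone, because the arms also differ in pre-operative nivolumab exposure and in time to chemotherapy and surgery. Extend it to pre-operative response, pathologic response and the biomarker comparisons.
3. In 12.1 and 12.3, replace the term standard treatment with mFOLFOX6 plus nivolumab.

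No change to doses, schedule, sample size, alpha or test is proposed. The cost is a narrower claim: a positive result would support the regimen, and the vaccine's own contribution would remain a question for a later design.

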5.5 Supportive Care

Anti- emetics: Moderate emetogenicity. Follow local anti-emetic policy.

Anti-diarrheals: Follow local anti-diarrheal policy.

Premedications for hypersensitivity: Not usually required unless the patient has had a previous hypersensitivity. H1 or H2 blockers or steroids as pre-medication or for chills/fever /rigor during the infusion if required.

Treatment of dermatologic reactions may include topical moisturizers (containing urea, salicylic acid or ammonium lactate), sunscreen (SPF>15 UVA/UVB), topical steroids (e.g. clobetasol), and topical (e.g. lidocaine) and/or oral pain relievers (e.g. ibuprofen, naproxen, or celecoxib). Advise patients to limit the use of hot water, take cool showers or baths, pat skin dry/avoid rubbing of hands or feet, apply ice packs or cool wet towels, avoid the sun/sources of heat, avoid harsh chemicals, avoid walking barefoot and wear loose-fitting clothing.

Mouthwashes (e.g. Caphasol, grade III mouthwash) may be prescribed for mucositis to be used as needed.

5.6 Reproductive Information

There is no information about how an immune response against CEA and MUC-1 might affect sperm function, egg function, or growth of an unborn baby. It is not recommended to become pregnant, breast feed, father children or donate sperm from the time of informed consent until 4 months after the last dose of vaccine. For those subjects, that do not receive the vaccine this is not applicable and information below provides timeframe for birth control.

Nonclinical findings suggest for Nivolumab a potential risk to human pregnancy. Hence, Nivolumab dosing during pregnancy is prohibited. In addition, women of childbearing potential (WOCBP) receiving Nivolumab will be instructed to adhere to contraception from the time of informed consent, during treatment and for 5 months after the last dose of Nivolumab. This timeframe is also applicable to breastfeeding. Men receiving Nivolumab are not required to use contraception but consideration should be given for the timeframe outlined per package insert for chemotherapy. This also applies to donation of sperm.

The two contraception methods can be comprised of two barrier methods, or a barrier method plus a hormonal method.

5.7 Concomitant Medications

All concomitant medications received within 28 days before the first dose of trial treatment and 30 days after the last dose of trial treatment should be recorded. Subjects who are still being followed for a serious adverse events (SAE) will have SAE-specific concomitant medications recorded until resolution of the SAE. For specific information regarding the use of concomitant medications with study drug(s) please refer to the appropriate IB.

5.7.1 Allowed Concomitant Medications

All treatments that the site investigator considers necessary for a subject's welfare may be administered at the discretion of the site investigator in keeping with the community standards of medical care. All concomitant medications will be recorded on the eCRF including all prescription, over-the-counter (OTC), herbal supplements, and IV medications and fluids. If changes occur during the trial period, documentation of drug dosage, frequency, route, and date may also be included on the eCRF.

5.7.2 Prohibited Concomitant Medications

Medications or vaccinations specifically prohibited in the exclusion criteria are not allowed during the ongoing trial. If there is a clinical indication for one of these or other medications or vaccinations specifically prohibited during the trial, discontinuation from trial therapy or vaccination may be required. The site investigator should discuss any questions regarding this with the sponsor-investigator via the HCRN project manager. The final decision on any supportive therapy or vaccination rests with the site investigator and/or the subject's primary physician. There are no prohibited therapies during the Post-Treatment Follow-up Phase.

The following medications are excluded while the subject is receiving study drugs:

- Any other HDAC inhibitor, including valproic acid
- DNA methyltransferase inhibitors
- Any additional anticancer agents, such as chemotherapy, immunotherapy, targeted therapy, biological response modifiers, or endocrine therapy, will not be allowed, even if utilized as treatment of non-cancer indications.
- Any therapeutic investigational agents
- Radiation therapy; **NOTE:** Radiation therapy to a symptomatic solitary lesion or to the brain may be considered on an exceptional case-by-case basis after consultation with Sponsor Investigator. The subject must have clear measurable disease outside the radiated field. Administration of palliative radiation therapy will be considered clinical progression.
- Traditional herbal medicines; these therapies are not fully studied and their use may result in unanticipated drug-drug interactions that may cause or confound the assessment of toxicity
- Live vaccines within 30 days prior to the first dose of trial treatment and while participating in the trial. Examples of live vaccines include, but are not limited to, the following: measles, mumps, rubella, varicella/zoster, chicken pox, yellow fever, rabies, BCG, and typhoid (oral) vaccine. Seasonal influenza vaccines for injection are generally killed virus vaccines and are allowed; however intranasal influenza vaccines (e.g. Flu-Mist[®]) are live attenuated vaccines, and are not allowed.
- Systemic glucocorticoids (>10 mg prednisone equivalent) for any purpose other than to modulate symptoms from an event of clinical interest of suspected immunologic etiology. Brief, limited use of systemic corticosteroids (≤ 7 days) are permitted where such use is considered standard of care (e.g. as premedication for contrast allergy or for COPD exacerbation). Inhaled or topical steroids, and adrenal replacement doses of steroids (for example prednisone 10mg daily) are permitted while on study.

